### **6.3 IM Group**

HIV-infected subjects in the IM Group will receive the first two doses of study drug in accordance with the Trogarzo® prescribing information (diluted in normal saline and administered over 15 minutes via IVI) at Day 1/Baseline and again at Day 15. The next four doses of Trogarzo® will be administered as an IM injection. At Day 85 (12 weeks), IM Group HIV-infected subjects will revert to diluted IVI dosing over 15 minutes in accordance with the Trogarzo® prescribing information.

HIV-uninfected individuals will receive four doses of Trogarzo® (pre-Steady State Phase) as described above for Core Group HIV-uninfected individuals prior to the Study Treatment Phase. In the Study Treatment Phase, HIV-uninfected subjects will receive the first two doses of Trogarzo® in accordance with the prescribing information (diluted in 250 mL normal saline and administered over 15 minutes via IVI) at Day 1/Baseline and again at Day 15. The next four doses of Trogarzo® will be administered as an IM injection.

HIV-uninfected subjects will discontinue dosing after the Day 71 study drug administration. The scheduled visit at Day 113 (16 weeks) for the HIV-uninfected IM Group subjects is for safety follow-up only, and this visit may be conducted by telephone if no clinic visit is needed for this purpose. Trogarzo® administration at Day 99/follow-up should be conducted in the routine manner as employed prior to the study, through the primary care provider. The Day 99 EOS visit in the

HIV-uninfected IM group subjects that is 28 days after the last dose of Trogarzo® must be completed in the clinic.

Safety assessments, including collection of blood and urine specimens for safety laboratory testing, as well as HIV-1 viral load and archive and viral resistance samples (HIV-infected individuals only), will be conducted every 2 weeks beginning at Day 1/Baseline and continuing through Day 85 [12 weeks]) for HIV-infected subjects, and through Day 99 for HIV-uninfected healthy volunteers. In addition, subjects will also have non-laboratory safety assessments (vital signs, recording of concomitant medications, assessment of IM injection site) conducted during visits on intervening weeks between the study IM drug administrations through the EOS. AEs are collected at all timepoints from time of consent.

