## **8. Adverse Events**

### **8.1       Definitions**

Per the FDA regulations in 21 CFR (Code of Federal Regulations) 312.32, the following definitions apply to this protocol:

**Adverse Events.** An AE is defined as any untoward medical occurrence associated with the use of a drug in humans, whether or not considered drug related.

**Adverse Reaction.** Any adverse event caused by a drug or its experimental administration.

**Treatment-Emergent AEs.** A treatment-emergent AE is defined as any event not present before exposure to study drug or its experimental administration or any event already present that worsens in either intensity or frequency following exposure to the experimental administration of study drug.

**Serious Adverse Event or Serious Suspected Adverse Reaction.** An adverse event or suspected adverse reaction is considered “serious” if, in the view of either the investigator or sponsor, it results in any of the following outcomes: death, a life-threatening adverse event, inpatient hospitalization or prolongation of existing hospitalization, a persistent or significant incapacity or substantial disruption of the ability to conduct normal life functions, or a congenital anomaly/birth defect. Important medical events that may not result in death, be life-threatening, or require hospitalization may be considered serious when, based upon appropriate medical judgment, they may jeopardize the subject or subject and may require medical or surgical intervention to prevent one of the outcomes listed in this definition.

**Suspected Adverse Reaction.** A suspected adverse reaction means any AE for which there is a reasonable possibility that the drug or its experimental administration caused the AE. For the purposes of IND safety reporting, “reasonable possibility” means there is evidence to suggest a causal relationship between the drug or its experimental administration and the AE.

**Unexpected Adverse Event or Unexpected Adverse Reaction.** An AE or adverse reaction that is not listed in the investigator’s brochure or is not listed at the specificity or severity that has been observed.

The Common Terminology Criteria for AEs (CTCAE) v. 5.0 scale will be used for assessment of any infusion reactions, or anaphylactic events (see [Section 8.5](#)). The DAIDS: Table for Grading the Severity of Adult and Pediatric AEs Version 2.1 will be used for assessment of all other AEs (see [Appendix B](#)).

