### **8.3 Reporting Adverse Events**

The investigator is responsible for reporting to the Sponsor or designee all AEs that are observed or reported by the subject during the study (from the time the subject signs informed consent until 28 days after the last dose of the administration of study drug is given whether by IV infusion, bolus, or push or IM injection), regardless of their relationship to study drug or its experimental administration or their clinical significance. Subjects will be instructed to contact study site personnel at any time after informed consent if any symptoms develop. AEs will be documented in the subject's source documents and recorded in the AE section of the EDC system.

To ensure compliance with FDA regulations (21 Code of Federal Regulations [CFR] 312.64), site investigators must report immediately all AEs that meet the SAE criteria, regardless of presumed relationship to the study drug or its experimental administration, to the Sponsor. The Sponsor will carefully review the SAE information to monitor the study drug's toxicity profile and subject safety. If any event meets the FDA's reporting criteria, it will be submitted to the FDA as an IND Safety Report (21 CFR 312.32).

All AEs reported or observed during the study must be recorded in detail in the AE section of the EDC system and followed to a satisfactory resolution or until the investigator deems the event to be chronic or the subject to be stable.

Information to be collected includes the event term, date of onset, date of resolution, investigator-specified assessment of severity and relationship to study drug or its experimental administration, and seriousness, as well as any required treatment or evaluations and outcome.

Pre-existing conditions (present before the start of the AE collection period) are considered concurrent medical conditions and should NOT be recorded as AEs. However, if the pre-existing condition worsens in severity, the investigator must report it as an AE.

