##### **4.3.2. AEs**

All AEs will be coded using MedDRA dictionary version 22.0. The use of another version will not be considered a violation of the SAP, nor require an amendment to the plan. All summary tables will be based on coded preferred terms (PTs), instead of verbatim terms. The categories and definitions of severity and causal relationship for

all AEs, including the criteria for which an AE is to be classified as “serious,” are as described in the protocol (Section 8).

A treatment-emergent AE (TEAE) is defined as any event not present before exposure to study drug or any event already present that worsens in either intensity or frequency following exposure to study drug. All AEs entered on the Adverse Events eCRF will be analyzed as TEAEs. A TEAE with missing severity or relationship will be considered severe or related, respectively.

The overall incidence of TEAEs will be summarized for all subjects in the SAF Population. The number and percentage of subjects having the following will be tabulated:

- TEAE
- Serious TEAE
- TEAE leading to discontinuation
- TEAE with outcome of death
- Suspected Adverse Reaction
- Severe (Grade 3 or 4) TEAE
- Class C TEAE per the Centers for Disease Control and Prevention (CDC) Classification System for HIV Infection

The overall incidence of TEAEs will also be summarized by System Organ Class (SOC), and by SOC and PT. The number and percentage of subjects reporting an event, as well as the number of events reported by the subjects will be tabulated. The incidence of serious TEAEs and TEAEs leading to study discontinuation (if any) will be summarized in the same manner. If there are multiple occurrences of the same TEAE within any SOC or PT for the same subject, only the first occurrence will be counted.

The incidence of TEAEs by severity/grade (Mild, Moderate, Severe, or Potentially life-threatening, Death) and by relationship to study drug (Suspected Adverse Reaction or Unrelated), and the incidence of serious AEs (SAEs) by relationship to study drug, will also be summarized.

All other AEs will be classified as non-TEAEs and identified in listings only. Serious TEAEs, TEAEs leading to study discontinuation, and TEAEs with an outcome of death will be presented in separate listings, if needed.

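### Both SAPs define treatment-emergent AEs by exposure, then count every AE on the eCRF as treatment-emergent, so pre-dose events can enter the TEAE tables but not the TEAE listings

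*SAP*

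**What the plan says.** SAP 4.3.2, in the same words in the IM and IV push plans, gives three rules:

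- The definition: "A treatment-emergent AE (TEAE) is defined as any event not present before exposure to study drug or any event already present that worsens" after exposure.
- The next sentence: "All AEs entered on the Adverse Events eCRF will be analyzed as TEAEs".
- At the end of the section: "All other AEs will be classified as non-TEAEs and identified in listings only".

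The section also treats a TEAE with missing severity as severe and one with missing relationship as related.

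Protocol 8.1 agrees with the definition: "A treatment-emergent AE is defined as any event not present before exposure to study drug or its experimental administration", or a pre-existing event that worsens afterwards.

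On collection, Protocol 8.3 requires all AEs, whatever their relationship to drug, "from the time the subject signs informed consent until 28 days after the last dose of the administration of study drug is given", and they are "recorded in the AE section of the EDC system". Protocol 6.3 says of the IM Group: "AEs are collected at all timepoints from time of consent". The Schedules of Events (Tables 1 to 4) mark AE recording at Screening. Their footnote 3 limits entries before the first dose to AEs related to study procedures.

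**The concern.** The second rule cannot be applied together with the other two. If every AE on the form is a TEAE, the definition does no work and the non-TEAE class is empty. A programmer has to choose which sentence to follow, and the mock tables and mock listings already point in different directions.

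Safety of the new route is a primary objective of both portions, and its analysis is descriptive, so the TEAE counts are themselves the result. An event that began before the first study dose cannot have been caused by on-study administration, by IM injection or by IV push. Counting it as treatment-emergent misstates the quantity that the tables are meant to show.

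**Working it through.** The plan states no figure on this point, so the check is a comparison of texts followed by a scale calculation.

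**Step 1. How each text treats an AE with onset after consent and before first dose**

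| Place | Treatment of that AE |
|---|---|
| SAP 4.3.2, definition (both SAPs) | Not a TEAE unless it worsens after exposure |
| Protocol 8.1 | Same |
| SAP 4.3.2, next sentence (both SAPs) | TEAE |
| SAP 4.3.2, closing rule (both SAPs) | Assumes that some AEs are non-TEAEs and only listed |
| IM Listings 16.2.7.1 to 16.2.7.3, footnote 1 | Excluded: cut at the date of first dose |
| IV push Listings 16.2.6.1 to 16.2.6.3, footnote 1 | Excluded: cut at the Day 1 visit |
| TEAE summary table shells (IM Tables 14.3.1.1.1 to 14.3.1.4.1; IV push Tables 14.3.1.1.1 to 14.3.1.1.3) | No date cut, so the all-AEs sentence governs and the event is counted |

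**Step 2. Whether such an AE can be on the form.** Collection begins at consent (Protocol 8.3 and 6.3), and Screening is a scheduled AE visit. Footnote 3 narrows what is entered before dosing but does not exclude it. The screening windows are:

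- HIV-infected: up to 28 days before Day 1.
- HIV-uninfected: Screening from Day -83 to Day -62 and first dose on Day -55, giving 83 − 55 = 28 days at most and 62 − 55 = 7 days at least.

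**Step 3. What the outputs would show.** A procedure-related event at Screening would be in the TEAE table and absent from the TEAE listing that should support it. If its relationship were missing, 4.3.2 would report it as related. If its severity were missing, 4.3.2 would make it severe, although the by-severity shell (for example IM Table 14.3.1.3.1, footnote 2) puts such events only in the any-grade column.

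**Step 4. A linked error in the opposite direction.** SAP 3.3.3 puts first dose at Day -55 for HIV-uninfected subjects. In the IV push portion these subjects receive four doses (Days -55, -41, -27 and -13) before Day 1. The IV push TEAE listings cut at Day 1 and would drop events that are treatment-emergent in that interval, including serious ones (Listing 16.2.6.2). IV push Table 14.3.1.1.3 has a Pre-Steady State column for the same interval, so here too table and listing would disagree. The IM listings cut at first dose and do not have this problem.

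**Step 5. Scale.** Each portion plans 20 subjects (section 3.1 of each SAP). One subject whose only AE is pre-dose changes total TEAE incidence by 1/20 = 5.0 percentage points.

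The documents give no pre-dose AE rate. If a proportion p of subjects has such an event, the chance of at least one among 20 is 1 − (1 − p)^20:

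| Assumed p | Chance of at least one in 20 |
|---|---|
| 2% | 1 − 0.98^20 = 33% |
| 5% | 1 − 0.95^20 = 64% |
| 10% | 1 − 0.90^20 = 88% |

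**The case against.** The best defence is that the plan's intention can be recovered. The non-TEAE class is retained and the listing footnotes apply a cut, so a careful programmer would probably exclude pre-dose events. Footnote 3 keeps their number low. No test or threshold depends on TEAE incidence: the dose-limiting-toxicity rules use 7- or 14-day windows after dosing, and study stopping depends on attribution confirmed by the DMC. The error adds events and does not hide harm. All of this stands. It limits the consequence, but it leaves in place a stated rule that is wrong and table shells that carry no cut.

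A reader might infer more than the documents support in four ways:

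- **That the definition is simply overridden.** It is contradicted. Other text in the same section and in the listings still follows it.
- **That pre-dose events cannot be due to drug.** HIV-infected subjects have normally had at least 3 months of commercial Trogarzo before entry (Protocol 4.5 and 5.1), so their screening events may be drug-related. What can be excluded is the on-study dose and the route under test. Only uninfected volunteers not yet dosed in the study are free of exposure before Day -55.
- **That the length of screening measures the inflation.** A 28-day window is a maximum share of calendar time. Treating it as a share of events would assume a constant AE rate and unrestricted recording, and footnote 3 restricts recording.
- **That by-period columns must add up to Total.** Subject counts need not, because one subject can have events in several periods. The diagrams defining the periods were not visible to me, and some IV push listing shells show screening or pre-treatment as example period values, so how a pre-dose AE is assigned to a period cannot be settled from the text.

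**Conclusion.** The rule is wrong as written in both SAPs. It contradicts the SAP definition, Protocol 8.1, the retained non-TEAE class and the first-dose cut in the IM listings. Applied literally, it puts pre-dose AEs into the TEAE tables and leaves them out of the TEAE listings, and it exposes them to the missing-relationship and missing-severity imputation.

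The size is 5 percentage points per affected subject at N = 20. The number of affected subjects is unknown and, under footnote 3, probably small. The 33% to 88% range for at least one affected subject rests entirely on assumed rates of 2% to 10%. The conclusion also takes first exposure to mean the first study dose, as SAP 3.3.3 does. It is worth correcting because safety is a primary objective and its tables are descriptive, but nothing in the stopping rules or PK criteria depends on it.

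**What to change.** 1. Delete the all-AEs sentence from 4.3.2 in both SAPs.
2. Flag a TEAE by onset or worsening on or after the first study dose: Day 1 for HIV-infected and Day -55 for HIV-uninfected subjects, as SAP 3.3.3 already has it.
3. List earlier AEs as non-TEAEs.
4. Apply that one cut to every TEAE table and listing. Add it as a footnote to the table shells, and replace the Day 1 cut in IV push Listings 16.2.6.1 to 16.2.6.3, which is wrong for uninfected Core subjects.
5. Reconcile Protocol 8.3 (all AEs from consent) with schedule footnote 3 (only procedure-related AEs before first dose), so that sites and programmers know what the pre-dose records contain.

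The cost is one deleted sentence and a revised flag in each SAP, footnote edits in the shells, and a protocol clarification. No new data are needed. Deleting the sentence alone would not be enough, because the IV push listing cut and the conflict in collection rules would remain.

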#### **4.3.3. Clinical Laboratory Parameters**

Summary statistics will be presented for laboratory measurements overall for all subjects in the SAF Population. The following analytes will be tabulated/listed:

- **Hematology:** complete white blood cell count with differential, hemoglobin, hematocrit, and platelets.

- **Serum chemistry profile:** albumin, alkaline phosphatase, alanine aminotransferase (ALT), amylase, aspartate aminotransferase (AST), blood urea nitrogen, calcium, chloride, creatine phosphokinase, creatinine, direct bilirubin, gamma glutamyl transferase, glucose, lactate dehydrogenase magnesium, phosphorus, potassium, sodium, total bilirubin, total protein, and uric acid. In addition, eGFR will be presented using the following formula:  $eGFR = 1.86 \times [Creatinine/88.4]^{-1.154} \times [Age]^{-0.203} \times [0.742 \text{ if female}] \times [1.210 \text{ if Black}]$ .
- **CD4+ Cell Counts**

Urinalysis results will be presented in a data listing and will include results from microscopic testing only. Pregnancy test, Serum Follicle-Stimulating Hormone (FSH) test, Hepatitis Serology, C-reactive Protein, Prothrombin Time and Partial Thromboplastin Time, and Viral Resistance Testing will also be presented in data listings only.

Normal ranges for the laboratory parameters will be provided by the laboratory that performed the assessments. All normal ranges will be standardized and results will be reported in standard units. The tables will include summary statistics for the assessments and the changes from Baseline to each subsequent time point of measurement. A table of subjects with abnormal (i.e., outside normal range) laboratory assessments will also be presented as a frequency of the incidence of each DAIDS toxicity grade (1 – 4) and route of administration.

Potentially Clinically Significant (PCS) criteria may be applied to laboratory parameters as clinically indicated, and if applied, will be summarized as described above. PCS is defined as a laboratory value that is lower or higher than a laboratory's normal range limits.

Note: Electronic clinical laboratory data will be received at Westat. Data reconciliation will be performed to resolve any discrepancies with the Oracle database. Details of data receipt will be described in the Data Receipt Plan.

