## 5.1 Inclusion Criteria

### HIV-infected participants:

Subjects must meet all of the following criteria to be included in the study:

1. Are capable of understanding and have voluntarily signed the informed consent document
2. Currently receiving a stable Trogarzo®-containing ARV regimen for a minimum of 3 months, and no change in background ARVs anticipated over the period of study participation; a stable regimen is defined as having no changes in dose or frequency and no interruptions  $\geq 2$  weeks during the 3-month period
  - Note: For subjects who receive Trogarzo® as an IV push (Core Group) and then enter the study to receive Trogarzo® as an IM injection (IM Group), the period while receiving the IV push will be considered as having received a stable Trogarzo®-containing ARV regimen.
  - Note: HIV-infected subjects who are enrolled in the IM injection study and are unable to adhere to the study schedule for IM dosing due to factors outside the study will be discontinued. Re-enrollment of HIV-infected IM Group subjects will be allowed after a Discontinuation Visit and Screening Visit are completed provided that inclusion/exclusion criteria continue to be satisfied and dosing after discontinuation is resumed according to the Trogarzo® Prescribing Information. For re-enrolling subjects, the inclusion criteria for stable a Trogarzo®-containing ARV regimen is satisfied with a loading dose of 2000mg IVI and at least one maintenance dose of 800mg IVI given according to Trogarzo® labeling prior to Day 1 enrollment.
3. Have no AIDS-defining events in the 3 months before Screening, other than cutaneous Kaposi's sarcoma or wasting syndrome due to HIV.
4. Are able and willing to comply with all protocol requirements and procedures
5. Are 18 years of age or older
6. Have a life expectancy that is  $>6$  months
7. Have a viral load  $<1,000$  copies/mL at Screening
8. CD4 $^{+}$  T-cell count  $>50$  cells/mm $^{3}$  at Screening

---

- 9. Prothrombin time (PT) and partial thromboplastin time (PTT) <1.5 times the upper limit of normal (IM Group only)

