**HIV-uninfected individuals:**

- 1. Healthy volunteers born male and female as assessed by medical history and physical examination
- 2. Aged  $\geq 18$  and  $\leq 50$  years at the time of Screening
- 3. Ability and willingness to provide written informed consent
- 4. Willingness to comply with protocol schedule
- 5. Willingness to undergo HIV-1 testing
- 6. Non-reactive 4th generation point of care HIV-1 test at Screening
- 7. Hepatitis B Surface antigen negative
- 8. Hepatitis C antibody negative, or if reactive, Hepatitis C RNA undetectable in plasma
- 9. PT and PTT <1.5 times the upper limit of normal (IM Group only)
- 10. Volunteers born female of reproductive potential who are sexually active with a male sex partner must agree to use one effective method of contraception from the time of signing the consent to completion of the study and agree to pregnancy testing as per the schedule of events.

Volunteers born female with reproductive potential are defined as pre-menopausal volunteers born female who have not had a sterilization procedure (e.g., hysterectomy, bilateral oophorectomy, tubal ligation or salpingectomy). Volunteers born female are considered menopausal if they have not had a menses for at least 12 months and have a follicle-stimulating hormone (FSH) of greater than 40 IU/L or if FSH testing is not available, they have had amenorrhea for 24 consecutive months.

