#### **HIV-uninfected individuals**

1. Confirmed HIV-1 infection
2. At high risk of severe COVID-19 disease as defined by one of the following:
  - History of hypertension, atherosclerotic cardiovascular disease (ASCVD), coronary artery disease, diabetes mellitus
  - History of asthma or chronic pulmonary disease
  - History of renal disease and chronic renal insufficiency
  - BMI over 35
3. Any acute or chronic medical condition that in the opinion of the investigator would preclude participation
4. Chronic autoimmune disease
5. Active IV drug use
6. Excessive use of alcohol or recreational drugs that in the opinion of the investigator would preclude participation
7. Decompensated psychiatric illness
8. Need for chronic immunotherapy including systemic corticosteroids, other MAb therapy, or immunosuppressive drugs
9. Volunteers born female who are pregnant, lactating, or planning on becoming pregnant over the study period
10. Any of the following laboratory parameters:
  - Hemoglobin <10.0 g/dL
  - Absolute neutrophil count <1,000/mm^3
  - Absolute lymphocyte count <500/mm^3
  - Platelet count <100,000/mm^3
  - Creatinine >1.25x upper limit of normal (ULN)
  - Aspartate aminotransferase (AST) >1.5x ULN
  - Alanine aminotransferase (ALT) >1.5x ULN
  - Glucose (non-fasting) >160 mg/dL
  - Proteinuria: 2+ or greater
  - Hematuria: >10 red blood cells (RBCs) per high-power field

11. Previous receipt of an experimental MAb for HIV-1 treatment or prevention in a research study
12. History of severe allergic reactions to drugs, vaccines, or drug infusion
13. Participation in another investigational clinical trial within the past 12 weeks or anticipated during the course of the current study
14. History of coagulopathy that would preclude administration of IM injections (IM Group only)
15. Skin rashes or tattoos that would prevent ability to assess IM injection for injection-site reactions (IM Group only)
16. Use of high-dose aspirin, clopidogrel, prasugrel, ticagrelor, dipyridamole or any other antiplatelet medication that would interfere with the ability to receive IM injections (IM Group only).

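### The eGFR formula printed in both SAPs, with leading constant 1.86, returns values near 1 for a normal creatinine in umol/L, and neither SAP states the creatinine or eGFR unit

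*SAP*

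**What the plan says.** Section 4.3.3 (Clinical Laboratory Parameters) of the IM SAP and the same section of the IV push SAP add a derived item to the serum chemistry list: "eGFR will be presented using the following formula". Both print the same expression. The leading constant is 1.86 and the creatinine term is printed as "Creatinine/88.4]^{-1.154". Age is raised to the power -0.203, with a factor of 0.742 for women and 1.210 for Black subjects.

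On units, the section says only "All normal ranges will be standardized and results will be reported in standard units". It names no unit for creatinine or for eGFR. The reference list in each SAP (section 5) holds the ICH E3 guideline and the bioequivalence guidance, with no source for an eGFR equation.

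The same section says that the laboratory tables will carry summary statistics and changes from Baseline at each later time point. Creatinine is listed there as an analyte in its own right.

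**The concern.** Dividing by 88.4 converts creatinine from umol/L to mg/dL, so a creatinine of 88.4 umol/L makes the bracket equal to 1. What remains for a non-Black man is 1.86 times a fractional power of age, which is close to 1 at any adult age. An eGFR near 1 is not credible for the people enrolled. The healthy volunteers, for example, are excluded if creatinine is more than 1.25 times the upper limit of normal (Protocol 5.2).

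Safety is a primary objective of both parts of the study. If the formula is programmed as printed, the report would contain an eGFR table with impossible values. The missing units add a second risk: a programmer given creatinine in mg/dL would get a different set of wrong values from the same line.

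**Working it through.** **Inputs from the documents**
- Constant 1.86, divisor 88.4, exponents -1.154 and -0.203, factors 0.742 (female) and 1.210 (Black): section 4.3.3 of each SAP.
- Ages: 18 to 50 for HIV-uninfected subjects; "Are 18 years of age or older" for HIV-infected subjects (Protocol 5.1).

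**Assumptions**
- Creatinine of 60-110 umol/L as a normal or near-normal range. The documents give no numeric range.
- Ages 25-65 for the range below, and 70 as the oldest age in the table.
- eGFR meant in mL/min/1.73 m2, with plausible values of about 60 to 120.

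The SAPs state no resulting eGFR value, so there is no figure of theirs to reproduce. The check is direct evaluation.

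**Formula as printed**

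eGFR = 1.86 x (Cr/88.4)^-1.154 x Age^-0.203 x (0.742 if female) x (1.210 if Black)

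**Step 1: one case.** Non-Black man, age 40, Cr = 88.4 umol/L. The bracket is 1 and 40^-0.203 = 0.473, so eGFR = 1.86 x 0.473 = 0.88.

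**Step 2: by age**, same creatinine, non-Black man:

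| Age | As printed | Constant x 100 |
|---|---|---|
| 18 | 1.03 | 103.4 |
| 40 | 0.88 | 88.0 |
| 50 | 0.84 | 84.1 |
| 70 | 0.79 | 78.5 |

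**Step 3: range.** For non-Black men the lowest value is at Cr 110, age 65 (0.62) and the highest at Cr 60, age 25 (1.51). With the formula's own sex and race factors the limits become 0.62 x 0.742 = 0.46 and 1.51 x 1.210 = 1.83.

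**Step 4: size of the discrepancy.** The multiplier needed to bring 0.88 to a target value is 68 for 60, 102 for 90, 114 for 100 and 136 for 120. Turned round, for the printed formula to return 90 at age 40, creatinine would have to be 1.6 umol/L, which is not physiological.

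**Step 5: other readings of the units**
- Creatinine entered in mg/dL. At 1.0 mg/dL the bracket term is (1/88.4)^-1.154 = 176.28, so the same man gets 0.88 x 176.28 = 155. At 0.7 mg/dL he gets 234, and at 1.2 mg/dL 126.
- Output in mL/s. 0.88 x 60 = 52.8 mL/min, still low for a man of 40 with a normal creatinine.

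**Step 6: what carries through.** The constant c multiplies every value, so an absolute change c(x1 - x0) is wrong by the same factor as the values. In a percent change, 100 x (c x1 - c x0)/(c x0), c cancels. Entering creatinine in mg/dL is also a constant multiplier (176.28), so it cancels too.

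**The case against.** The strongest reply is that this is an obvious typographical slip with little consequence. Much of that stands. eGFR is an added derived item and is not in the protocol's own chemistry list (Protocol 7.2.1). Renal eligibility for volunteers uses creatinine itself. The toxicity plan and stopping rules (Protocol 4.3 and 4.4) and the PK analyses do not name eGFR. Creatinine is summarised separately with change from Baseline, so the renal safety information survives. A wrong constant can be rescaled without new data. The programming notes for the mock tables in both SAPs require quality checks, a column of values near 1 would be conspicuous, and no eGFR program code is given that would lock the figure in. These points set the severity. They do not make the printed rule right, and nothing elsewhere in either SAP corrects it. The same constant appears in both SAPs, so a misreading of one of them is unlikely.

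The second objection concerns the input unit. The mock shells are mixed: tables show BUN in mg/dL and hemoglobin in gm/dL, while example listings in the IV push SAP show bilirubin in umol/L and hemoglobin in g/L. If the creatinine data arrive in mg/dL, the printed formula gives values around 155, which are too high. That is a fair limit on any claim about direction. It does not rescue the formula, because the 88.4 divisor would then be the mistake.

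**Conclusion.** The concern holds as a minor one. With creatinine in umol/L, the printed formula gives an eGFR near 1 for a normal creatinine, roughly two orders of magnitude below a plausible value in mL/min/1.73 m2. Tabulated values and absolute changes from baseline would be wrong in both parts of the study if the formula were coded as printed.

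Three stronger readings are tempting, and the documents do not support them:
- **That every adult would get a value below 1.** At 88.4 umol/L a non-Black man scores 1.03 at age 18, and the race factor takes a man of 40 to 0.88 x 1.210 = 1.06. Near 1 is the accurate description.
- **That every eGFR would be exactly 100-fold too small.** The factor is the intended constant divided by 1.86, and the documents give neither that constant, nor the source equation, nor the eGFR unit. The claim also fails if creatinine is entered in mg/dL.
- **That the renal safety assessment or a trial decision is compromised.** Percent changes, creatinine summaries, eligibility, stopping rules and PK conclusions do not depend on the constant.

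The conclusion rests on the umol/L reading implied by the divisor, the assumed creatinine range and the assumed eGFR unit.

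**What to change.** In section 4.3.3 of both SAPs, and in the analysis program:
- Check the leading constant against the source equation and correct it. A two-place decimal shift would turn 0.88 into about 88 in the example, but the source should decide.
- Cite that equation in section 5.
- Confirm the unit in which creatinine is received, then state the creatinine input unit and the eGFR output unit beside the formula. If the data are in mg/dL, the 88.4 divisor also has to be reconciled.

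The cost is one figure, one reference and a line on units in each SAP, plus a check of the program. No new data are needed.
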